2.1 Background

This Data Analysis Plan describes the strategy, rationale and statistical methods that will guide assessment of the clinical efficacy and safety of anacetrapib in the REVEAL trial.

REVEAL is a randomized trial investigating the effects of adding the CETP-inhibitor anacetrapib to effective LDL-lowering treatment with atorvastatin. Over 30,000 participants with pre-existing atherosclerotic vascular disease were randomized between anacetrapib 100 mg daily versus matching placebo, with scheduled median follow-up of about 4 years. At the initial Screening visit, eligible individuals were given Run-in medication consisting of placebo anacetrapib and active atorvastatin, and asked to return to the clinic in 8-12 weeks (see Figure). At the Randomization visit, eligible and consenting individuals were randomly allocated anacetrapib 100 mg or matching placebo, along with active atorvastatin at the same dose started at the Screening visit. The primary aim is to assess the effect of anacetrapib on the composite outcome of major coronary event (MCE), defined as coronary death, myocardial infarction or coronary revascularization (see Section 4.1). The key secondary aim is to assess the effect of anacetrapib on coronary death, myocardial infarction or presumed ischaemic stroke (see Section 4.2). Other secondary, tertiary and exploratory assessments (including analyses of safety and biochemical efficacy) are described in Sections 4.2 to 4.7.

[figure not shown]

Figure. Outline of randomization and follow-up schedule

In November 2015 (after approximately 3 years' median follow-up), the independent Data Monitoring Committee (DMC) considered whether there were reasons to recommend early stopping for efficacy and futility. In summary, for efficacy, the DMC was to consider whether the randomized comparisons in the study provided (i) "proof beyond reasonable doubt" that prolonged use of anacetrapib reduces the primary outcome of major coronary events (with consistent results

in key subgroups), as well as coronary death or myocardial infarction, and cardiovascular mortality, with a consistent effect on all-cause mortality; and (ii) evidence that might reasonably be expected to influence materially patient management.

For futility, the DMC was to consider whether continuing the trial was likely to demonstrate any clinically meaningful effects of anacetrapib. For example, a positive result at 4.0 years median follow-up would be unlikely if at 3 years median follow-up and at least 70% of the anticipated total number of primary and secondary events, (i) the hazard ratio for the primary endpoint is greater than 0.95, (ii) there is no evidence of a treatment effect for those patients with >3 years follow-up, and (iii) there are no promising results for any major subgroup (e.g. diabetics, low baseline HDL-cholesterol) or for any major outcome (e.g. coronary death, myocardial infarction or presumed ischaemic stroke). However, the DMC was requested to consider also the possibility that greater benefits might emerge with prolonged follow-up. (For example, the benefits of statin therapy in the first year of treatment are about half those seen in each subsequent year of treatment).

The DMC recommended to the Steering Committee that the trial continue without modification.

3 Roles and Responsibilities

All analyses for reports, presentations and publications will be prepared by the coordinating centre at the Clinical Trial Service Unit, University of Oxford (the regulatory sponsor of the REVEAL trial).

4 Comparisons of anacetrapib versus placebo

All comparisons will involve comparing outcome during the scheduled treatment period (i.e. from date of randomization to date of final follow-up regardless of whether the participant continues on study treatment or not) among all those participants allocated at randomization to receive anacetrapib 100 mg daily versus all those allocated to receive matching placebo (i.e. “intention-to-treat” analyses).^{a,b1-3} Unless otherwise indicated, analyses will be of the first occurrence of the specified outcome. For those events that were subject to adjudication (see Protocol), analyses include all confirmed and unrefuted events.

4.1 Primary assessment

The primary assessment will involve an intention-to-treat comparison among all randomized participants of the effects of allocation to anacetrapib versus placebo on the incidence of major coronary events (defined as the occurrence of coronary death, myocardial infarction or coronary revascularization procedure) during the scheduled treatment period.

4.2 Secondary assessments

Secondary assessments will involve intention-to-treat comparisons among all randomized participants of the effects of allocation to anacetrapib versus placebo during the scheduled treatment period on:

- (i) Major atherosclerotic events (defined as coronary death, myocardial infarction or presumed ischaemic stroke; the key secondary outcome);
- (ii) Presumed ischaemic stroke (i.e. not known to be haemorrhagic); and

^a Following investigation of a serious breach of good clinical practice at one centre (centre id 3314), the Steering Committee determined (blind to knowledge of any unblinded results) at its meeting in February 2014 that all data from this centre should be excluded from all analyses.

^b A single censoring date is to be used in the REVEAL analyses for both fatal and non-fatal events. The censoring date is to be determined according to the flow-chart in Appendix A. Censoring rule.

- (iii) Major vascular events (defined as coronary death, myocardial infarction, coronary revascularization or presumed ischaemic stroke).

In addition, each of the individual components of the primary outcome (i.e. coronary death; myocardial infarction; and coronary revascularization) will be tested separately.

4.3 Additional assessments

These assessments (which have been specifically requested prior to the start of the study by regulatory agencies) will involve intention-to-treat comparisons among all randomized participants of the effects of allocation to anacetrapib versus placebo during the scheduled treatment period on:

- (i) Cardiovascular death or myocardial infarction; and
- (ii) Cardiovascular death, myocardial infarction or stroke.

4.4 Tertiary assessments

Tertiary assessments will involve intention-to-treat analyses among all randomized participants of the effects of allocation to anacetrapib versus placebo during the scheduled treatment period on:

- (i) Coronary death or myocardial infarction, and, separately, myocardial infarction alone
- (ii) Mortality
 - from all causes combined; and, separately, within particular categories of causes, i.e.:
 - all cardiovascular causes combined; and, separately:
 - coronary (including sudden cardiac death)
 - other cardiac
 - stroke
 - other vascular
 - all non-cardiovascular causes combined; and, separately:
 - cancer
 - infection
 - respiratory
 - hepatic
 - other medical*
 - non-medical

* including undetermined cause

- (iii) Stroke
 - of any type combined; and, separately, of particular types, i.e.:
 - confirmed ischaemic stroke
 - confirmed haemorrhagic stroke
 - stroke of unknown/unconfirmed aetiology
- (iv) Major coronary events, major atherosclerotic events, and major vascular events, separately, in various subdivisions:
 - (a) occurring more than one year after randomization;
 - (b) disease type prior to randomization:
 - coronary heart disease
 - cerebrovascular disease

REVEAL Data Analysis Plan

- peripheral arterial disease
- diabetes*

and timing of most recent qualifying vascular event: <12; ≥12 months

* diabetes at randomization is defined as self-reported diabetes recorded on screening or randomization form; or diabetes-related adverse event recorded on or before date of randomization; or use of hypoglycaemic medication reported on randomization form

(c) three similar-sized groups based on lipid and lipoprotein measurements* from the Randomization visit:

- HDL cholesterol (mmol/L): <0.9; ≥0.9<1.1; ≥1.1
- LDL cholesterol (mmol/L): <1.4; ≥1.4<1.7; ≥1.7
- total cholesterol (mmol/L): <3.2; ≥3.2<3.7; ≥3.7
- non-HDL cholesterol (mmol/L): <2.2; ≥2.2<2.6; ≥2.6
- triglycerides (mmol/L): <1.2; ≥1.2<1.7; ≥1.7
- apolipoprotein B (mg/dL): <60; ≥60<70; ≥70
- apolipoprotein A1 (mg/dL) <110; ≥110<125; ≥125
- lipoprotein (a) (nmol/L): <15; ≥15<55; ≥55

* using results measured in the central laboratory

(d) various other categories of participant based on their Randomization visit values:

- age (years): <65; ≥65<70; ≥70
- sex: male; female
- region: North America; Europe; Asia
- blood pressure (mmHg):
 - systolic <125; ≥125<140; ≥140
 - diastolic <75; ≥75<85; ≥85
- kidney function
 - estimated Glomerular Filtration Rate (ml/min/1.73m²) derived using the CKD-EPI equation⁴: <60; ≥60
 - urinary albumin:creatinine ratio (mg/mmol): normo-albuminuria (<3); micro-albuminuria (≥3 <30); macro-albuminuria (≥30)
- alcohol intake: current drinker; former/never drinker
- cigarette smoking: current; former; never
- body mass index (kg/m²): <25; ≥25<30; ≥30
- waist:hip ratio: low (<0.87 in women; <0.94 in men); medium (≥0.87<0.93 in women; ≥0.94<1.00 in men); high (≥0.93 in women; ≥1.00 in men)
- history of heart failure: yes; no
- atorvastatin dose (mg): low (10 in China; 20 in rest of the world); high (20 in China; 80 in rest of the world)

(e) presence and absence of other treatments used at the Randomization visit:

- angiotensin-converting-enzyme inhibitors or angiotensin-receptor blockers:
- aspirin or other antiplatelet drugs
- diuretics
- calcium-channel blockers
- beta-blockers

(v) Urgent and non-urgent coronary revascularization, considered separately and combined;

(vi) Non-coronary revascularizations, including percutaneous interventions (with or without stenting), surgical revascularization procedures (e.g. grafting, endarterectomy), and amputation for presumed vascular disease;

- (vii) Hospitalization for heart failure;
- (viii) Development of diabetes mellitus* among those not known to be diabetic at randomization (see section 4.4.iv.b);
 - * development of diabetes is defined as a post-randomization diabetes-related adverse event; or use of hypoglycaemic medication reported on at least one follow-up form
- (ix) Combination of first and subsequent occurrences of the primary outcome;
- (x) Cancer (fatal or non-fatal combined, and excluding any known to pre-date randomization and non-melanoma skin cancers)
 - at all sites combined; and, separately, at particular sites
 - gastrointestinal
 - respiratory
 - breast
 - melanoma
 - genitourinary
 - haematological
 - other or not specified
- (xi) Serious adverse events (overall and by subtype) due to:
 - Infection at all sites combined; and, separately, at particular sites:
 - Respiratory
 - Renal and urinary
 - Gastrointestinal
 - Skin
 - Systemic (including septicaemia)
 - Other or unspecified
 - Respiratory disease of all types combined; and, separately, of particular types:
 - Bronchial
 - Pulmonary vascular
 - Pleural
 - Other lower respiratory tract
 - Upper respiratory tract
 - Other respiratory

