5.3 Tests for heterogeneity of effects

Tests for heterogeneity of the proportional effect observed in subgroups will be used (whilst controlling the false discovery rate to allow for multiple comparisons) to determine whether the proportional effects in specific subcategories are clearly different from the overall effect.^{2,3} If, however, patient categories can be arranged in some meaningful order (e.g. age at randomization: <65; ≥65<70; ≥70) then assessment of any trend will be made. Unless otherwise stated, those with missing values of baseline values will be included in the subgroup that includes the median (for continuous variables) or the largest group (for categorical variables), and the number of missing values will be clearly indicated.

When a number of different subgroups are considered, chance alone may lead to there being no apparent effect in several subgroups in which the effect of treatment really is about the same as is observed overall. In such circumstances, “lack of direct evidence of benefit” is not good “evidence of lack of benefit”, and clearly significant overall results would provide strong indirect evidence of benefit in some small subgroups where the results, considered in isolation, are not conventionally significant (or, even, perhaps, slightly adverse).^{2,3,5} Hence, unless the proportional effect in some specific subcategory is clearly different from that observed overall, the effect in that subcategory is likely to be best estimated indirectly by applying the proportional effect observed among all patients in the trial to the absolute risk of the event observed among control patients in that category.⁵

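### Does listing overlapping disease types as one subgroup item make the heterogeneity test in SAP section 4.4(iv)(b) invalid?

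*SAP*

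**What the plan says.** Section 4.4(iv) calls for major coronary, major atherosclerotic and major vascular events to be examined in several subdivisions. One is "b) disease type prior to randomization", with four bullets: coronary heart disease, cerebrovascular disease, peripheral arterial disease and diabetes. The same item then adds the time since the most recent qualifying vascular event, split at 12 months. No levels are written beside the four conditions. By contrast, history of heart failure is given as yes or no, and item (e) is headed "presence and absence of other treatments used at the Randomization visit".

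Two other statements bear on overlap. Section 2.1 says "Over 30,000 participants with pre-existing atherosclerotic vascular disease were randomized". The footnote to item (b) defines diabetes without reference to vascular disease: "diabetes at randomization is defined as self-reported diabetes recorded on screening or randomization form", or by a diabetes-related adverse event or hypoglycaemic medication.

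On testing, section 5.3 says "Tests for heterogeneity of the proportional effect observed in subgroups will be used (whilst controlling the false discovery rate to allow for multiple comparisons"). The aim is to judge "whether the proportional effects in specific subcategories are clearly different from the overall effect". It gives no test statistic, no degrees of freedom and no rule for overlapping groups.

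**The concern.** Read literally, item (b) is one factor with four categories, and those categories cannot be exclusive. A participant with diabetes also has vascular disease, and someone with coronary disease may well have cerebrovascular or peripheral arterial disease too. The usual heterogeneity chi-square for four groups assumes independent estimates. When the same events count under two or more headings, the estimates are positively correlated and the statistic no longer follows chi-square on 3 degrees of freedom.

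The question matters clinically. The futility guidance in section 2.1 names diabetics as an example of a major subgroup, and section 5.2 may place emphasis on subgroup results for major vascular events. Under section 5.3, a subgroup not clearly different from the whole is assigned the overall proportional effect, so an insensitive test would push towards finding no difference. Its P-value would also enter the false-discovery-rate procedure. The number of tests that item (b) contributes is not stated either.

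**Working it through.** **Inputs.** The SAP gives no event target, prevalences or power for subgroup tests, so there is no figure of its own to reproduce. Taken from the SAP: log-rank estimation, two-sided 5%, four headings and three outcomes. Assumed: 3,500 events; interaction ratios of 1.15, 1.25 and 1.4; shares of events of 72-99% for coronary, 16-53% for cerebrovascular, 5-43% for peripheral arterial disease and 20-60% for diabetes.

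**What a naive pooled test would do.** Let S_i be observed minus expected events under heading i, V_i its variance (events/4), and

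Q = Σ S_i²/V_i − (Σ S_i)²/Σ V_i.

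Let k be the number of headings that a participant falls under. With no heterogeneity, E(Q) = 4 − E(k²)/E(k), averaged over events.

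- Exclusive headings, k = 1: E(Q) = 4 − 1 = 3, as a chi-square on 3 degrees of freedom requires.
- Vascular types exclusive, diabetes 20%: E(k) = 1.20; E(k²) = 0.80 + 0.20 × 4 = 1.60; E(Q) = 4 − 1.60/1.20 = 2.67.
- Vascular types exclusive, diabetes 37%: E(k) = 1.37; E(k²) = 0.63 + 0.37 × 4 = 2.11; E(Q) = 4 − 2.11/1.37 = 2.46.

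Q is too small on average, so the test is conservative. Simulation (200,000 runs per case) gives the level at nominal 5%:

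| Shares of events | True level |
|---|---|
| Four exclusive groups (calibration) | 5.0% |
| Vascular types exclusive, diabetes 20% | 3.4% |
| Vascular types exclusive, diabetes 37% | 2.7% |
| 96 / 24 / 9 / 37% | 1.2% |
| 85 / 53 / 43 / 60% | 0.07% |

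(Order in the last two rows: coronary, cerebrovascular, peripheral, diabetes.) The level does not depend on the overall treatment effect.

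**Power in the 96 / 24 / 9 / 37% case, 3,500 events, diabetes interaction:**

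| Ratio | Naive 3 df | 3 df allowing for covariance | Yes/no, 1 df |
|---|---|---|---|
| 1.15 | 9% | 35% | 51% |
| 1.25 | 36% | 76% | 89% |
| 1.4 | 87% | 99% | 99.8% |

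Hand check of the 89%: the variance of the difference in log rate ratios is 4/(3,500 × 0.37) + 4/(3,500 × 0.63) = 0.00309 + 0.00181 = 0.00490, so the standard error is 0.0700. Then ln(1.25)/0.0700 = 0.2231/0.0700 = 3.19, and power = Φ(3.19 − 1.96) = Φ(1.23) = 0.89. Of the 53-point gap at 1.25, 40 points (36 to 76) come from ignoring overlap. The other 13 (76 to 89) come from using 1 degree of freedom aimed at the right factor. Yes/no tests had a level of 4.9-5.1% in every scenario.

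**Does the SAP plan the naive test?** Set the relevant places side by side.

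- Section 5.3 does not pool these headings. It asks whether a subcategory differs from the overall effect.
- Item (b) also holds the timing split, so it is a container and not a single variable.
- In items (c), (d) and (e) each bullet is its own factor. The drug classes in (e) plainly overlap, and nobody would read them as one five-level variable.
- Section 4.4(viii) studies new diabetes "among those not known to be diabetic at randomization (see section 4.4.iv.b"), which uses item (b)'s definition as a two-level variable.
- The section 5.3 rule for missing values (join the largest group) works for a two-level variable.

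**Size of the false-discovery-rate family.** Per outcome, items (c), (d) and (e) hold 8 + 13 + 5 = 26 factors, and timing makes 27. Item (b)'s disease list adds 1 or 4, giving 28 or 31. Assuming a 5% rate and a Benjamini-Hochberg procedure applied per outcome, the strictest threshold is 0.05/28 = 0.0018 or 0.05/31 = 0.0016.

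**The case for a change.** The best case for acting is that the disease list is the only part of items (b) to (e) without stated levels, that it covers a clinically prominent question, and that one line would settle it. Left open, the layout and the number of tests could be chosen after unblinding, and a naive analysis would miss real differences.

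Part of this stands. The levels are not written, overlap with diabetes is certain, and a naive pooled test would be miscalibrated even if the three vascular types were exclusive. Overlap among the vascular types is likely, though the SAP does not state it.

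The rest is weaker. Invalidity belongs to a test that the plan does not contain. The power loss varies widely with the assumptions: in the 96 / 24 / 9 / 37% case it is large at ratios of 1.15 to 1.25, but at 1.4 it is only 87% against 99.8%. The powers are also taken at nominal 5%, whereas section 5.3 works under false-discovery-rate control. The freedom over the family barely moves the threshold, as shown above. A conservative P-value entering that procedure does not create false findings.

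**Conclusion.** The concern does not call for a change. The four headings do overlap, and a 3-degree-of-freedom chi-square across them would be too conservative, with a level of roughly 0.1% to 3.4% over the assumed prevalences. The SAP does not specify that test, and the reading that best fits sections 4.4 and 5.3 is four conditions, each present versus absent, for which the standard test is valid. An analyst used to log-rank subgroup displays would lay it out that way without being told.

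If someone did pool the headings, the error would be a missed difference in a tertiary analysis that section 5.3 already treats with caution. It would not be a false claim, and the primary and key secondary comparisons would not move. The numerical sizes rest on assumed event counts, prevalences and interaction ratios. The conclusion itself rests on the text and would be the same for any of them.

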4.5 Additional safety assessments

Additional safety assessments will include intention-to-treat analyses among all randomized participants of the effects of allocation to anacetrapib versus placebo during the scheduled treatment period on:

- (i) blood pressure-related outcomes:
 - blood pressure at 12 months and at final follow-up visit
 - mean level of systolic blood pressure (SBP) and diastolic blood pressure (DBP)
 - level of SBP (<140; ≥140<160; ≥160<180; ≥180 mmHg) and level of DBP (<90; ≥90<100; ≥100<110; ≥110 mmHg)
 - change from randomization in SBP and DBP (in each case <-10; ≥-10<0; ≥0<10; ≥10 mmHg)
 - serious adverse events due to hypertension
- (ii) muscle-related outcomes:

REVEAL Data Analysis Plan

- creatine kinase [CK] >5x and ≤10x laboratory upper limit of normal [ULN] plus ALT >1.5x ULN
- CK >10x and ≤40x ULN overall and, separately, with muscle symptoms
- CK >40x ULN overall and, separately, with evidence of end-organ damage, such as doubling of serum creatinine (i.e. rhabdomyolysis[°])

(iii) liver-related outcomes:

- ALT >3x ULN plus bilirubin >2x ULN, with CK ≤5x ULN
- ALT >3x ULN on 2 occasions within about one week (i.e. 1 to 14 days), with CK ≤5x ULN
- liver injury (i.e. ALT >3x ULN plus bilirubin >2x ULN; ALT >10x ULN [regardless of bilirubin level]; liver transplantation; or death due to liver disease) by cause*

* causes to be classified as: known (e.g. infection; alcohol; cancer; drug-related [excluding randomized anacetrapib/placebo]); and unknown (including cases believed due to study treatment with no alternative cause identified)

(iv) renal function at final visit

- estimated glomerular filtration rate (eGFR)
 - difference in mean eGFR
 - development of impaired renal function (i.e. eGFR <60ml/min/1.73m²) among those with normal renal function (i.e. eGFR ≥60ml/min/1.73m²) at randomization.
- albuminuria
 - development of albuminuria (urinary albumin:creatinine ratio [uACR] ≥3 mg/mmol) in those with normo-albuminuria at randomization
 - development of macro-albuminuria in those with normo- or micro-albuminuria at randomization.

(v) discontinuation of study treatment* overall and, separately, by various causes

- serious adverse events**
- non-serious adverse events**
- other reasons (various categories; e.g. cannot attend clinic, participant concern, medical advice, administrative reason)

* reason recorded at time of latest discontinuation (without any subsequent restart)

** categorised by assigned System Organ Class (see section 5.6)

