5.1 Methods of analysis

All participants randomized to anacetrapib will be compared with all participants randomized to placebo, regardless of whether a participant received all, some or none of their allocated treatment (i.e. intention-to-treat [ITT] analyses).^{2,3} A participant may contribute to more than one assessment if they have events of more than one type (e.g. non-fatal ischaemic stroke followed by coronary death). For the time-to-event analyses, survival analytic methods will be used to evaluate the time to the first event during the entire study period. For each outcome, log-rank method will be used to estimate the average event rate ratio comparing all those allocated active anacetrapib with all those allocated placebo.³ Estimates of the event rate ratio will be shown with 95% confidence intervals. Kaplan-Meier estimates for the time to each of the primary and secondary outcomes will also be plotted (with their associated log-rank p-values). Cox regression may be used where rate ratios are extreme (e.g. > 2 or < 0.5). In all analyses, two-sided p-values (2P) < 0.05 will be considered statistically significant (after any allowance for multiplicity as outlined in section 5.2).

Recurrent events will be analysed using the negative binomial and sensitivity analyses will be performed using alternative methods such as the Andersen-Gill approach.

At the time of finalizing the Data Analysis Plan in May 2016, around 99% of the 28,613 surviving randomized participants had attended their most recent scheduled visit. Since loss-to-follow-up at study end is anticipated to be minimal (<1%), no exploratory analyses investigating the impact of missing data not at random/informative missingness are planned.

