5.5 Analysis of safety and biochemical outcomes

For each of the events listed as additional safety outcomes (section 4.5), the number of randomized participants with at least 1 event will be compared using standard tests for differences in proportions. For analyses of continuous variables, differences in means between the randomized groups will be assessed (unless otherwise specified). Exploratory analyses will be conducted among particular categories of participant. For participants selected for blood sampling who were alive at the time of the scheduled follow-up assessment but failed to provide a sample, LDL- and HDL-cholesterol values will be imputed based on baseline and 2 month values while taking into account their background atorvastatin and reported compliance.

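### Albuminuria at the final visit is compared only through two upward threshold crossings; a pre-specified baseline-adjusted comparison of log uACR should be added beside them

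*SAP*

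**What the plan says.** SAP section 4.5(iv), renal function at the final visit, has two parts.

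- **eGFR:** a full-scale comparison, "difference in mean eGFR", and a threshold outcome (falling below 60 ml/min/1.73m²).
- **Albuminuria:** "development of albuminuria (urinary albumin:creatinine ratio [uACR] ≥3 mg/mmol) in those with normo-albuminuria at randomization" and "development of macro-albuminuria in those with normo- or micro-albuminuria at randomization". No mean, geometric mean or log-uACR comparison is listed.

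The uACR classes (cuts at 3 and 30 mg/mmol) are set in section 4.4(iv)(d). For events listed in 4.5, section 5.5 says that "the number of randomized participants with at least 1 event will be compared using standard tests for differences in proportions". Section 5.5 also gives a general rule of comparing means for continuous variables, but 4.5 does not list uACR as one.

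**The concern.** uACR is a continuous measurement, and the two planned rows already need it at randomization and at the final visit. Reducing it to two crossings discards three things: movement within a class, any fall, and all final values from participants with macro-albuminuria at randomization. The plan avoids this for eGFR by pairing the clinical cut with a mean.

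Because this is a safety assessment, the cost of inefficiency is a null result read as more reassuring than it is. A modest general rise (or fall) in albumin excretion could go undetected, and no listed row would estimate its size.

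**Working it through.** The SAP states no power, crossing rate, standard deviation or effect size for albuminuria, so there is no figure of its own to reproduce.

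**Inputs from the SAP.** Cuts at 3 and 30 mg/mmol (4.4(iv)(d), 4.5(iv)); two-sided 0.05 (5.1); more than 30,000 randomized (2.1).

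**Assumptions, not in the SAP.** Final urine samples N = 20,000-26,000 in total; share normo-albuminuric at randomization a = 65-80%; share macro-albuminuric b = 3-6%; correlation of baseline and final log uACR r = 0.5-0.75; log uACR normal; the same proportional shift in everyone.

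**Step 1: who contributes.**

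| Class at randomization | Row 1 (reaches 3) | Row 2 (reaches 30) | Log-uACR row |
|---|---|---|---|
| Normo | yes | yes | yes |
| Micro | no | yes | yes |
| Macro | no | no | yes |

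A micro-albuminuric participant whose uACR falls counts in row 2 exactly as one who stays put.

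**Step 2: formulas.** Let n = N/2 per arm and δ = ln(1 + shift).

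- SD of log uACR: σ = ln 10 / [z(1−b) − z(a)].
- Crossing 3 mg/mmol from below: p0 = 1 − Φ₂(z(a), z(a); r)/a for placebo. For p1, replace the second argument by z(a) − δ/σ.
- Power of the 3 mg/mmol test: Φ(|p1−p0| / √{[p0(1−p0)+p1(1−p1)]/(an)} − 1.96).
- Power for mean log uACR, unadjusted: Φ((δ/σ)√(n/2) − 1.96).
- Power for mean log uACR, baseline-adjusted: the same with δ/σ divided by √(1−r²).

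**Step 3: one case in full** (N = 20,000, a = 80%, b = 3%, r = 0.5).

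- σ = 2.3026/(1.8808 − 0.8416) = 2.216; p0 = 0.1411; an = 8,000 per arm.
- A shift of 15.1% (δ = 0.1404) gives p1 = 0.1568. Difference/SE = 0.01577/0.005628 = 2.80, so power is 80%.
- Unadjusted log uACR: (0.1404/2.216) × 70.71 = 4.48, so power is 99.4%.
- Adjusted: 4.48/√0.75 = 5.17, so power is 99.9%.
- At a 5% shift (δ = 0.0488) the three powers are 16%, 34% and 44%.

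**Step 4: all combinations of the assumed ranges.**

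| Setting | 3 mg/mmol test | Unadjusted log uACR | Adjusted log uACR |
|---|---|---|---|
| Shift giving the 3 mg/mmol test 80% | 80% | 98-99% | over 99% |
| Shift of 5% | 10-43% | 19-72% | 23-97% |

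Implied placebo crossing rates are 10-24%. At the first setting the macro-albuminuria test has 36-58%. The order cut < unadjusted < adjusted holds in every combination.

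**Step 5: dependence on the reference point.** Step 4's first line cannot show a gain above 20 points, because it starts from 80%. Now fix the log comparison at 80% instead, in the same participants. The relative efficiency of a cut is φ(c)²/[p(1−p)], where c = z(1−p) and p is the crossing proportion. Power of the cut is Φ(2.80 × √efficiency − 1.96).

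| p | Efficiency | Power of cut | Loss (points) |
|---|---|---|---|
| 50% | 0.637 | 61% | 19 |
| 20% | 0.490 | 50% | 30 |
| 10% | 0.342 | 37% | 43 |

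**Step 6: where the gain disappears** (assumed 10,000 per arm, 10% crossing).

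- Relative risk of crossing 1.10: 64% for the cut against 97% for the unadjusted mean.
- Relative risk 1.20: 99.5% against 100%.
- Effect confined to 2% of participants, each shifted by 2 SD: p1 = 0.98 × 0.10 + 0.02 × 0.764 = 0.1133. The cut has 86% and the mean (0.04 × 70.71 = 2.83) has 81%.
- With a right-skewed log distribution (N = 20,000), the 3 mg/mmol test at 80% power and the effect confined to the upper half of underlying uACR, the unadjusted mean ranged from a 10-point loss to a 7-point gain. The adjusted mean still gained about 17 points.

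**The case against.** The strongest case for leaving the plan alone has four parts.

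1. **Threshold-only reporting is not peculiar to uACR.** CK, ALT and bilirubin in section 4.5 are also continuous and assessed only by multiples of the upper limit of normal. This stands. A reader might infer that uACR is the lone exception in 4.5, and it is not. The contrast that holds is with eGFR in the same item, and with blood pressure in 4.5(i), each of which gets means as well as categories.
2. **The plan does not forbid the analysis.** The list in 4.5 is open, 4.7 allows further exploratory work, and 5.5 has a rule for means. So it is too strong to say that a net shift cannot be estimated; it is not pre-specified. That still matters, because 5.2 makes the weight given to a comparison depend on whether it was pre-specified.
3. **The planned test is not weak in absolute terms.** Under the same assumptions the 3 mg/mmol test has 80% power for a relative increase of about 8-14% in new albuminuria. The SAP sets no power target here, and mean eGFR already gives a continuous renal comparison. This stands and limits the severity.
4. **The cuts are the plan's own clinical classes.** Excluding participants with macro-albuminuria at randomization is inherent in counting its development. This stands, and is why the existing rows should stay.

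It is also tempting to state a fixed loss of some 17-20 points. The documents do not support one. Such a figure follows either from holding the cut at 80% power, which caps the gain at 20, or from assuming that half the participants cross. Other assumptions give more, almost nothing, or a reversal.

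**Conclusion.** The point holds as a minor one. As written, albuminuria is compared only through two upward crossings, although the plan needs the continuous values at both visits and treats eGFR on its full scale. For a general proportional shift this loses power under every combination of assumptions tried. The size cannot be fixed from the SAP, and all power figures here rest on assumed sample numbers, class shares, correlation, log-normality and a uniform effect. The advantage is negligible for large effects and is not guaranteed for effects confined to a small fraction or to the upper tail. Nothing in the SAP is contradictory on this point, and neither the primary nor the secondary assessments are touched.

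**What to change.** Add one pre-specified row to section 4.5(iv), next to the two existing albuminuria rows and without ranking it above them:

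*Difference between randomized groups in mean log uACR at the final visit (ratio of geometric means, 95% CI), adjusted for log uACR at randomization, among all participants with a final urine sample; values below the assay limit set to that limit.*

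Both threshold rows stay as the clinical description; they may also be the more sensitive view if an effect is confined to a few participants.

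Cost: one SAP line and one table row, from urine results that the existing rows already require. The downsides are one more safety p-value and a scale less familiar to clinicians than new albuminuria.
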